8.1.2 Event Censoring

- For efficacy endpoint in section 3.2.1 bullet 1 (population sensitization threshold), an individual's true threshold is
 - left censored if individual fails on the smallest dose administered
 - right censored if no adverse effect is observed on the largest dose administered
 - interval censored in all other cases.
- For the latter three time to loss of desensitization efficacy endpoints defined in section 3.2.1 bullet 2, censoring is defined as below:
 - Subjects with 48th month LOAEL < MCRT who are not administered the final DBPCFC have their time to loss of desensitization assumed to be zero.
 - Subjects with the final DBPCFC NOAEL equal to the highest administered dose level are assumed to have their LOAEL beyond the observed time.
 - For subjects who do not show up for the final DBPCFC until the 17th week of randomization will be removed from the analysis. A separate analysis will be conducted to predict drop-outs.

No censoring will occur on safety endpoints.

8.1.3 Data Handling for Patients who withdraw from the Study

Such subjects will be considered intolerant and failing at time 0.

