#### ***Primary Objective:***

First, we aim to estimate the population sensitization threshold, the dose predicted to provoke reactions in X% of the peanut-allergic population after at least 48 months of peanut SLIT treatment. Second, given the above estimated population sensitization threshold and the administered dose levels that it lies between, we would like to characterize the SU curve with respect to time for several end points including time for desensitization threshold as assessed by the final DBPCFC to reduce by half of the estimated sensitization threshold, to drop by a level of the administered dose level, to remain above minimal clinically relevant threshold (MCRT) and finally, to maintain threshold constancy.

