#### **3.3 Premature Intervention Halting, Termination or Participant Withdrawal**

##### **3.3.1 Criteria**

No subject initiating SLIT in this trial will be replaced.

Participants may be withdrawn from the SLIT study drug and/or the protocol if:

- Significant clinical symptoms (respiratory, GI, skin) are experienced at home after taking the study drug daily dose
- Poor control or persistent activation of secondary atopic disease (e.g. atopic dermatitis, asthma)
- Non-adherence with home dosing protocol (i.e., excessive missed dosing days or missed appointments) would be a safety issue warranting discontinuation

- Started on Angiotensin II Receptor Blockers ARBs, ACE inhibitors, beta-blockers, or other prohibited medications with no alternative options per the prescribing physician, will be withdrawn from study
- Pregnancy. A serum pregnancy test will be performed at the onset of menses, and a history of the menstrual cycle will be obtained at regular intervals. Urine pregnancy tests will be performed prior to DBPCFCs and at any other time point if warranted. Participants who become pregnant will be withdrawn from the study drug and may remain in follow-up.
- The participant (parent) elects to withdraw consent from all future study activities, including follow-up
- The participant is “lost to follow-up” (i.e., no further follow-up is possible because attempts to reestablish contact with the participant have failed)
- The participant dies

Participants who prematurely stop study drug interventions (i.e., study drug) for any reason, may continue in follow-up.

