### **5.2 Enrollment**

Up to 55 children may be enrolled in this protocol, including the participant allowed under an exception to enroll from the CoFAR 4 Pro0003579 (not counted in the data analysis for this study). Accounting for a 10% drop out rate, we anticipate having approximately 45 children eligible for randomization during the blinded phase of the study.

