4.3 Method of Week Assignment for the Final Challenge and Randomization

The following criteria must be satisfied in order for the patient to continue to the SU phase of the study and be randomized:

1. The patient achieves MCRT at the 48th month DBPCFC to continue to the SU phase. This requires patient to be asymptomatic upon administration of 300 mg dose as assessed by Food Challenge Symptom Score sheet.
2. If subjects are found symptomatic and AEs that occur are considered to be intolerable at or below the MCRT, subjects will be refrained from taking the final challenge and will be considered to have lost their desensitization at week 0.
3. No subject will be administered a final challenge dose higher than the NOAEL attained at the 48th month DBPCFC.

Before the start of the SU phase of the study, a computer-generated block randomization schedule is prepared such that each subject has an equal probability of being randomized to one of the weekly challenges held in initial 6 weeks, between 7-12 weeks and between 13-17 weeks. Based on the randomization schedule, three qualified subjects are randomly assigned to one of the final DBPCFC administered each week during the study's 17-week SU phase.

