To illustrate, we introduce the following notation. Let X_d be the time to loss of desensitization with distribution F_d for a given NOAEL, d , administered at the 48th month DBPCFC ($d = 100, 200, 500, 800, 1300, 2100$ mg). Let T be an observation time (in weeks), $t = 0, 1 \dots 17$ with distribution G . Because the assignment time is randomized, the time of interest X_d and baseline covariates will be independent of T . We also assume that the clinically induced desensitization is monotonically decreasing such that the subject's NOAEL is either decreased or stays constant by observation time T . In other words, the true time to loss of desensitization from the 48th month DBPCFC, which is unknown, is either less or equal to the observation time. This could mathematically be represented as a problem of case-1 interval censoring wherein, we observe n i.i.d observations of $(T, I\{X_d \leq T\} | d) = (T, \Delta_d)$ for a given NOAEL, d . Further, we assume $X_d = 0$ for those subjects who do not meet MCRT ($d < MCRT$) at the 48th month DBPCFC. Let π define the probability that $X_d = 0$, and let the baseline and clinical covariates be represented by Z . Then, in order to derive the likelihood of F_d , we need to solve the following optimization problem to find the MLE:

$$\sup_{F \in \mathcal{F}} L_n(F)$$

, where \mathcal{F} is a class of distribution functions and

$$L_n(F) = \prod_{i=1..n} P(\beta, \gamma, Z_i, t)$$

$$\begin{aligned} P(\beta, \gamma, Z_i, t) &= \{P(X_{id} = 0) I(X_{id} = 0)\} * \{P(X_{id} > 0) I(X_{id} > 0)\} \\ &* \{P(X_{id} = t, \Delta = 0 | d, X_{id} > 0)\} * \{P(X_{id} = t, \Delta = 1 | d, X_{id} > 0)\} \\ &= \left[\frac{e^{\gamma' Z_i}}{1 + e^{\gamma' Z_i}} \right]^{y_i} * \left[\frac{1}{1 + e^{\gamma' Z_i}} \right]^{1-y_i} * [(1 - F_d(t))g(t)]^{1-\delta_i} * [F_d(t)g(t)]^{\delta_i} \\ &= \left[\frac{e^{\gamma' Z_i}}{1 + e^{\gamma' Z_i}} \right]^{y_i} * \left[\frac{1}{1 + e^{\gamma' Z_i}} \right]^{1-y_i} * (1 - F_d(t))^{1-\delta_i} * F_d(t)^{\delta_i} g(t) \end{aligned}$$

$$y_i = I(X_{id} = 0); \delta_i = I(\Delta_i = 1); F_d(t) = 1 - e^{-\lambda_i t}; \lambda_i(t, Z_i) = \lambda_0 e^{\beta' Z_i}$$

Maximizing the above likelihood will provide estimates of β & γ towards estimating distribution of time to loss of desensitization.

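### SAP 8.1.3 gives every study withdrawal the code of an observed month-48 failure, and it conflicts with SAP 7, 4.3 and 8.1.2 on who is analysed and how

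*SAP*

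**What the plan says.** **The withdrawal rule.** SAP 8.1.3 says of children who withdraw: "Such subjects will be considered intolerant and failing at time 0". It does not separate withdrawal during build-up, maintenance or avoidance, or one reason from another. Protocol 3.3.1 lists reasons related to tolerating the drug (significant symptoms after home doses) and reasons that need not be, such as starting a prohibited medicine, loss to follow-up, or this one: "The participant (parent) elects to withdraw consent from all future study activities, including follow-up".

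**What time 0 already means.** Three places in the SAP use it for a failed month-48 challenge:
- 4.3 item 2: children with intolerable symptoms at or below the MCRT "will be considered to have lost their desensitization at week 0".
- 8.1.2: children whose month-48 LOAEL is below the MCRT, and who get no final challenge, "have their time to loss of desensitization assumed to be zero".
- 10.1: X_d is set to 0 "for those subjects who do not meet MCRT" at the month-48 challenge, and pi is the probability that X_d = 0.

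**Other rules for missing outcomes.** SAP 8.1.2 has a different rule for the final challenge: "For subjects who do not show up for the final DBPCFC until the 17th week of randomization will be removed from the analysis". SAP 8.1.4 fails a child with intermittent missing efficacy data at the first missing time, not at time 0.

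**Who is analysed.** SAP 7 runs all efficacy analyses in the ITT population, defined as randomized patients. SAP 4 places randomization at the month-48 visit, and SAP 4.3 makes reaching the MCRT a condition for it. The primary objective in the protocol concerns the threshold "after at least 48 months of peanut SLIT treatment".

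**The concern.** A child who leaves in the second year has no month-48 result. Giving that child the code of a month-48 failure turns dropout into evidence about desensitization. Pi would then be partly a dropout rate. Gamma, which is meant to show which children desensitize, would mix predictors of failure with predictors of leaving. The proportion with loss of desensitization at a fixed time takes on the same error.

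A child who passed at month 48 and withdrew during avoidance presents a clearer problem, because here the code contradicts data. The pass was observed, and SAP 8.1.2 would remove a child who never attends the final challenge. The SAP does not say which rule prevails.

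**Working it through.** **1. The dropout input.** The documents' only dropout rate is 10% (Protocol 5.2, "Accounting for a 10% drop out rate", and Protocol 8.1.1). Protocol 8.1.1 uses it to reach 50 subjects in the original two-arm design, and that figure reproduces. Take 90% v 50%, 1:2 allocation, two-sided 0.05, 80% power and no continuity correction:

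- pooled proportion = (0.9 + 2×0.5)/3 = 0.633
- n (SLIT) = [1.96×√(1.5×0.633×0.367) + 0.8416×√(0.9×0.1 + 0.5×0.5/2)]² / 0.4² = 14.96, so 15
- total = 15 + 30 = 45, and 45/0.9 = 50

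This check has no bearing on 8.1.3 beyond supplying the 10%. Applied to the 51 enrolled, 0.10×51 = 5.1, so about 5 children.

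**2. The sections side by side.**

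| Child | Month-48 result | SAP 8.1.3 | Other SAP sections | In ITT if SAP 7 and 4.3 are read strictly |
|---|---|---|---|---|
| Challenged, below MCRT | failure observed | not a withdrawal | time 0 (4.3, 8.1.2, 10.1) | no, not randomized |
| Left before the challenge | none | time 0 | no rule | no, not randomized |
| Passed, withdrew before final challenge | pass observed | time 0 | removed (8.1.2) | yes |

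The first two rows receive the same code with different information behind it. In the third row two rules disagree. The last column shows that the set which excludes early leavers also excludes the observed failures that define pi in 10.1.

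**3. What the code does in the likelihood.** In 10.1, y = 1 when X_d = 0, and the child contributes e^(γ'Z)/(1+e^(γ'Z)). A withdrawal coded 0 therefore contributes exactly what an observed failure does. Without covariates, the estimate of pi is the share coded 0. With N enrolled, W withdrawn before month 48 and failure rate f among the N − W challenged:

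P(X=0) = [f(N − W) + W]/N

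The documents give no month-48 failure rate, so f is assumed over a range.

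| Assumed f | 51 enrolled, 5 withdrawn | 55 enrolled, 10 withdrawn |
|---|---|---|
| 5% | (2.3+5)/51 = 14.3% | (2.25+10)/55 = 22.3% |
| 10% | (4.6+5)/51 = 18.8% | (4.5+10)/55 = 26.4% |
| 20% | (9.2+5)/51 = 27.8% | (9+10)/55 = 34.5% |
| 30% | (13.8+5)/51 = 36.9% | (13.5+10)/55 = 42.7% |

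The second scenario takes the synopsis figures of 55 accrued and 45 completing (10/55 = 18.2%) and places all the loss before month 48, so it is an upper case. The added amount is about 7 to 9 points in the first scenario and 13 to 17 in the second. Since 1 − P(X=0) = (1 − W/N)(1 − f), the proportion still desensitized at any week is multiplied by 46/51 = 0.902 in the first.

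**4. The strict reading.** If only randomized children count, early leavers add nothing. But every randomized child has then reached the MCRT, so observed failures number zero and P(X=0) consists only of later withdrawals. With an assumed 5 such withdrawals among 45, it is 5/45 = 11.1% against 0% observed.

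**The case against.** The strongest reply is that SAP 7 already settles the matter. Efficacy is analysed in randomized patients, randomization takes place at month 48, and a child who left earlier is in no efficacy analysis. SAP 4 even allows a coherent version in which all children challenged at month 48 are randomized at that visit and those who fail simply have no final challenge. Also, X_d in 10.1 is defined for a given month-48 NOAEL, which an unchallenged child does not have.

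Much of this stands. It is not established that early leavers will enter pi, and a reader should not infer that they certainly will. But SAP 4.3 makes reaching the MCRT a condition for randomization, which contradicts the coherent version. It also assigns three children to each of 17 weeks; 3×17 = 51 is the whole enrolment, with no allowance for failure or dropout. The sections do not define one efficacy set, and 8.1.3 is the only rule written for withdrawals. Nor does the reply help with children who passed and then withdrew, since they are in ITT on any reading.

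A second reply is that counting withdrawals as failures is a recognised conservative choice. That is fair for pi if declared, and leaving early leavers out has a cost, because some may have left through dosing symptoms. It does not justify the effect on gamma, where the direction of the error is unknown.

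Two stronger inferences are tempting. One is that withdrawn children become first-dose reactors and pull ED05 and ED10 down. The text does not support this: 8.1.3 assigns a time, not a dose, and left-censoring in 8.1.2 and 10.1 requires a failure on the smallest dose administered. The other is that families declining the amended design would produce many coded failures. The documents give no refusal rate.

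**Conclusion.** The concern holds as an unrestricted rule that pools withdrawals with observed failures and conflicts with other sections. For children without a month-48 challenge the effect depends on the reading. It is zero if SAP 7 excludes them. If it does not, P(X=0) rises by about 7 to 9 percentage points, assuming that the 10% dropout all falls before month 48 and that failure among challenged children is 5% to 30%. For children who passed and then withdrew, the contradiction with the observed result and with 8.1.2 is in the text; its size depends on how many there are, which the documents do not say. No effect on ED05 or ED10 is claimed. The point should be settled before database lock.

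**What to change.** 1. Define the primary efficacy set as all children with a month-48 DBPCFC, including those below the MCRT, and align SAP 7 with it.
2. State that 8.1.3 does not apply to children without a month-48 DBPCFC. Leave them out of ED05/ED10, pi and gamma, and the time-to-loss likelihood, and tabulate them by reason and time on SLIT.
3. For children who passed at month 48 and withdrew before the final DBPCFC, keep the month-48 result (y = 0) with no current-status contribution, consistent with 8.1.2.
4. Add two sensitivity analyses: one counting all withdrawals as failures, and one counting only those related to dosing symptoms or intolerance.

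The cost is SAP wording and two extra runs. No new data are needed, since SAP 9.1 already tabulates reasons for withdrawal. The downside is that the main estimate applies to children who reached the month-48 challenge and may be favourable if intolerant children left earlier. The sensitivity analyses show by how much, and the report should state the restriction.

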8.1.4 Imputation of Missing Data

No missing safety data will be imputed. For efficacy data with intermittent missingness, a subject will be considered failed at the first time when missingness is encountered.

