We have incorporated strong steps in the protocol to be implemented during the study's conduct to ensure minimization of bias due to unblinding and of missing data during the off-SLIT period. We have created a provision for patients who fail to show up on their randomized final food challenge to continue to participate in the clinical trial, providing outcome data during regularly scheduled visits. In addition, multiple analysis techniques are included in this SAP to examine the outcomes of interest and the robustness of results.

In summary, the two-fold objectives are to estimate the population level threshold for desensitization and study the TLD given a desensitization dose level and subjects' characteristics. The proposed primary efficacy analyses deal with special cases of interval censored data using parametric and semi/non-parametric methods of estimation that have been carefully chosen to address the primary questions of interest. A detailed discussion of the primary efficacy analysis approach is presented in Section 10.1.

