3.2 Study Endpoints

3.2.1 Efficacy Endpoints

The primary efficacy endpoints are:

- An estimate of the dose as assessed by the 48th month DBPCFC, also called population sensitization threshold, predicted to provoke reactions in 5% and 10% of the peanut-allergic population. This will also give population level NOAEL and LOAEL that would define interval of consecutive administered dose levels within which the population sensitization threshold lies.
- Multiplicative or differential change in the population sensitization threshold as assessed by the 48th month DBPCFC with a unit change in covariates.
- An estimate of time to loss of desensitization for the following events:
 - Subject's true sensitivity threshold to reduce by half, also called half-life of sensitivity threshold.
 - Subject's true sensitivity threshold to maintain at the same level of LOAEL.
 - Subject's true sensitivity threshold to drop by at least one level of LOAEL.
 - Subject's true sensitivity threshold to remain at or above MCRT.
- Estimates of the proportion of patients at a fixed time for any of the above events that define loss of desensitization (bullet 2).
- Multiplicative change in hazard of loss of desensitization with a unit change in covariates.

Secondary efficacy endpoints include:

- Comparative estimates of changes in immune parameters over time among subjects who were induced with clinical desensitization versus those who failed.

- Incidence of all serious adverse events (SAEs) during the study.

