4.5 Minimization of Missing Data due to Missed Visits during Tolerance Phase

To ensure minimization of missing data during the SU phase, the trial has been designed to encourage patient retention through multiple approaches, including provision of the possibility of "re-randomization" if more than one subject of the assigned week miss the visit they are scheduled at; or allowing a subject to take the final challenge on the study's next scheduled visit. The importance of minimizing the amount of missing data has been discussed with all study investigators, and their awareness of the importance of patient compliance and minimal dropout rates is factored into their recruiting plans. In addition, investigators are advised to contact the medical monitor for guidance on available management options when needed to prevent patients from withdrawing from the study.

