8.1.1 Statistical Assumptions

Time to Loss of Desensitization (TLD) requires more rigorous mathematical framework of stochastic process. However, a good approximation could be achieved using Interval Censoring framework for the latter three events defined in section 3.2.1 (bullet 3). The framework uses following assumptions:

- Desensitization is monotonically decreasing with time. $NOAEL(\text{final DBPCFC}) \leq NOAEL(48\text{th month DBPCFC})$
- Subject's true sensitivity threshold at the 48th month DBPCFC is approximated by his/her NOAEL.
- Subjects with the final DBPCFC NOAEL higher than the 48th month DBPCFC NOAEL will be regarded as exceptions. Their final DBPCFC NOAEL will be considered equal to the 48th month DBPCFC NOAEL for conservative time to loss of desensitization estimates.
- Subjects with 48th month LOAEL < MCRT will also fail at LOAEL administered at the final DBPCFC that are less than MCRT, thereby un-necessitating the need for the final DBPCFC.
- Since the final DBPCFC observation times are randomized, subject's unobserved time to loss of desensitization and the baseline covariates are independent of his/her final DBPCFC observation time.

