8.2.2 Change in Immune Parameters

There are numerous parameters: peanut specific IgE, peanut specific IgG4, skin test size, basophil reactivity, TH2 cytokine release, and T regulatory levels. These were drawn annually and at the final challenge(s).

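### SAP 8.1.4 read literally codes a child who misses the assigned week but passes a later permitted challenge as a loss, against the SAP's own monotonicity assumption and its late-attendance provisions

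*SAP*

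**What the plan says.** - **SAP 8.1.4 (Imputation of Missing Data):** "For efficacy data with intermittent missingness, a subject will be considered failed at the first time when missingness is encountered". The sentence covers efficacy data in general.
- **SAP 4.5 (Minimization of Missing Data):** two remedies are offered for a missed visit in the avoidance phase. One is re-randomization "if more than one subject of the assigned week miss the visit they are scheduled at". The other is "allowing a subject to take the final challenge on the study's next scheduled visit".
- **SAP 1 (Background):** patients who do not appear for their randomized final challenge are "to continue to participate in the clinical trial, providing outcome data during regularly scheduled visits".
- **SAP 8.1.2 (Event Censoring):** children who have still not attended by week 17 are dropped from the time-to-loss analysis.
- **SAP 8.1.3 (withdrawals):** subjects who withdraw count as failures at time zero.
- **SAP 8.1.1 (Statistical Assumptions):** "Desensitization is monotonically decreasing with time". The same section takes the final-challenge time to be independent of the unobserved time to loss, because that time is randomized.
- **SAP 10.1:** time to loss is analysed as case-1 interval censoring. Each child contributes one observation time T and one indicator of whether loss has occurred by T.
- **SAP 10.2:** continuous secondary endpoints, which include the immune parameters, are analysed by MMRM. BOCF/LOCF applies to values after treatment discontinuation or withdrawal.

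**The concern.** Each child has one planned challenge after avoidance. Withdrawal and never attending have their own rules (8.1.3 and 8.1.2). For the time-to-loss endpoint, the obvious remaining case for 8.1.4 is a child who misses the assigned week and is challenged later, which is the case SAP 4.5 creates. On its plain words, 8.1.4 then replaces an observed result with a failure at the missed week.

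Three things are at stake.

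- **Time to loss is a primary estimate in a single-arm phase.** With no control arm, nothing offsets a downward bias. Protocol 2.1 expects the duration result to bear on dosing interval and the effect of missed doses, so calling the rule conservative does not justify it.
- **Covariate effects on the hazard of loss are also primary (SAP 3.2.1).** If missing a visit is itself an event, any covariate linked to missed visits will look like a predictor of loss.
- **Two analysts could follow the SAP and report different primary results,** because no text ranks 8.1.4 against 4.5 and 8.1.2.

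**Working it through.** **Step 1: logic.** Suppose a child is assigned week 6, misses it, and passes at week 9. The week-9 pass means the time to loss X is greater than 9. Under monotonicity (SAP 8.1.1) X is therefore also greater than 6. Literal 8.1.4 records X ≤ 6, an event that the model excludes.

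**Step 2: inputs.**

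- Model: F(t) = 1 − exp(−λt), from SAP 10.1, here without covariates.
- Observation weeks: t = 1, …, 17 with equal weight (SAP 4.3 plans three children per week).
- Children entering the avoidance phase: about 45 (Protocol 5.2).
- Share m who miss the assigned week: **assumed** 5%, 10%, 20%.
- True median: **assumed** 8, 17, 34 weeks.
- Late attenders are taken to be otherwise typical: **assumed**.

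The documents give no figure for late attendance or for its effect, so there is no plan figure to reproduce here. The stated minimum of 50 subjects belongs to the superseded two-arm design and does not enter.

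**Step 3: formula.** With true rate λ₀ = ln 2 / median, the probability of a coded event at week t under literal 8.1.4 is

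p(t) = m + (1 − m)(1 − exp(−λ₀t)).

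The large-sample estimate λ solves the current-status score equation

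Σₜ [ p(t) · t · exp(−λt) / (1 − exp(−λt)) − (1 − p(t)) · t ] = 0,

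and the fitted median is ln 2 / λ.

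**Step 4: one case in numbers.** True median 8 weeks, m = 10%: λ₀ = 0.693/8 = 0.0866. The average event share over weeks 1–17 rises from 49.9% to 0.10 + 0.90 × 0.499 = 54.9%. The score equation gives λ = 0.1001, so the fitted median is 0.693/0.1001 = 6.9 weeks.

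**Step 5: results.** Fitted median in weeks, with percentage shortening:

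| True median | 5% late | 10% late | 20% late |
|---|---|---|---|
| 8 | 7.4 (7%) | 6.9 (13.5%) | 6.0 (25%) |
| 17 | 14.8 (13%) | 13.0 (23%) | 10.3 (39%) |
| 34 | 26.4 (22%) | 21.4 (37%) | 15.1 (56%) |

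With a true 17-week median and 10% late, estimated retention at week 17 falls from 50% to 40.5%. Of 45 children, 45 × 0.10 = 4.5 would be late. About 68% of them, roughly 3, would pass one week later and still be coded as losses. Each false event moves the crude proportion by 1/45 = 2.2 percentage points.

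**Step 6: check of the alternative.** In simulation at n = 45 (800 runs per setting), the observed result one week late gave median estimates of 7.9–8.0 weeks (true 8), 17.0–17.3 (true 17) and 34.7–35.8 (true 34). The 8.1.4 coding reproduced the shortening in the table.

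**The case against.** The strongest reply is that the SAP never intended late passers to be losses. SAP 4.5 allows the later challenge in order to avoid missing data, section 1 keeps no-shows in the trial to supply outcomes, and 8.1.2 removes only those who never attend by week 17. In the likelihood of 10.1, a child challenged late has an observed time and an observed status, so arguably nothing is missing; a re-randomized child simply has a new assigned week. This stands in part. A reader might infer that the SAP settles that late passers count as losses. It does not: it contains two incompatible instructions. But 8.1.4 is a stated rule with no exception, so the conflict has to be resolved in writing.

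Three further readings go beyond the documents.

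- **A missed blood draw makes a child a failure.** Immune parameters are listed under efficacy endpoints in SAP 8.2, so 8.1.4 reaches them literally. But the MMRM of 10.2 has no failure status, and nothing says that a missed draw changes challenge status. No child is shown to move between the groups in "Comparative estimates of changes in immune parameters over time among subjects who were induced with clinical desensitization versus those who failed".
- **Late attendance is the only possible intermittent missingness.** A missing symptom score, or a dose not taken within the six-dose challenge, is another route. Failing a child at the first missing dose is a coherent use of the rule.
- **Attending late is always treated worse than not attending.** This holds against a child who stays in the trial but never attends, who is removed. It does not hold against a child who withdraws, who fails at time zero.

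The size is also open to challenge: no document gives a late-attendance rate, and the 10% in Protocol 5.2 and 8.1.1 is dropout.

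**Conclusion.** The point holds as a conflict within the SAP, with a biased result if 8.1.4 is followed to the letter. For the time-to-loss endpoint the rule can override an observed pass and record an event that 8.1.1 rules out, and the direction of that error is towards faster loss. Across the assumed settings the fitted median is 7% to 56% too short; for a true 8-week median the range is 7.4 down to 6.0 weeks.

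These sizes rest on the exponential form, uniform weeks, late attenders who are otherwise typical, and assumed rates and medians. They are illustrative. They also apply only if 8.1.4 prevails over 4.5 and 8.1.2, which the SAP leaves open. Because a primary estimate depends on the answer, it should be settled before database lock.

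**What to change.** Replace the second sentence of SAP 8.1.4 with wording to this effect:

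1. **Primary time-to-loss analysis.** A child who takes the final challenge late or after re-randomization contributes the observed result, with T equal to the actual weeks off SLIT.
2. **Sensitivity analysis.** Repeat the analysis with such a child coded as failed at the assigned week. Lateness may be informative, and the randomization argument for independence of T in 8.1.1 does not automatically cover a week that was not the assigned one. The sensitivity analysis gives a deliberately pessimistic bound.
3. **Scope.** State that 8.1.4 does not apply to immune parameters. Their intermittent missing values stay missing and are handled by the MMRM likelihood in 10.2.
4. **Related rules.** Reconcile 8.1.2 (never attended: removed) with 8.1.3 (withdrawn: failure at time zero), and say which applies to a child who withdraws during avoidance before being challenged. Removal should also be squared with the ITT definition in SAP 7, which includes everyone randomized.

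The cost is SAP wording and one extra model run. No change to visits, procedures or sample size is needed; the actual challenge date must be available in the analysis data.
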